#### DATA AND SAFETY MONITORING PLAN

The Principle Investigator (PI, [name]) and Faculty Advisor ([name], PhD) will be responsible for monitoring the data and safety of participants along with their co-investigators.

a. Periodic Review: The PI and faculty advisor will hold bi-weekly meetings for the first two months of enrollment, then monthly for four more months, and quarterly thereafter. The faculty advisor will review all minor AE and SAE reported to date of review. The staff meetings will include the PI, co-investigators, and lay co-workers in charge of assessment. The meetings will include evaluation of all research procedures, fidelity to protocol, discussion of newly enrolled participants, and review of status of all formally enrolled participants including all adverse events. Adverse events will be reviewed to determine if changes in the protocol are indicated. Participant demographics to date, recruitment progress, difficulties encountered during enrollment, an update on data entry, and any other issues or concerns that have arisen since the last research team meeting will also be discussed.

In addition to review of all research procedures and AE/SAE, specific review of risk related to behavioral condition of the patient and related to the intervention will be completed at meetings. Review will assess:

1. Risk to behavioral condition: Weekly checks via Zoom video conferencing of behavioral tracking will occur with PI and participants. If substantial behavioral change is noted by caregiver or patient report, this behavior change will be reviewed with faculty advisor.

2. Risk of Intervention: Weekly checks via Zoom video conferencing with participants will assess adverse events and patient complaint related to the intervention tools. We anticipate the following potential areas of concern:

- a. Lotions-minor dermatological reaction
- b. Exercise cards-muscle soreness, fall during exercise
- c. Snacks-possible choking hazard
- d. Actigraph wear-skin irritation at wear site (wrist)
- e. Scents of lotion-headache
- f. Gel lap pad-strain from lifting 3 pound lap pad.

b. Adverse Events: In compliance with Federal Regulation 21CFR §56.108(b)(1) and 45 CFR 46.103(b)(5), any unanticipated problems, including adverse events that are unexpected and related to the study, will be promptly reported to the University Institutional Review Board (IRB). Events judged as "unexpected" are those not specified in the IRB-approved research protocol or informed consent document.

The Data and Safety Monitoring Plan for the proposed project incorporates the policies on human subject data and safety monitoring specified by the University of Kentucky IRB.

Risk Assessment: Minimal risk. The study procedures and intervention represents minimal risk to study participants as this study intervention is a combined environment-based educational/sensory stimulation and standard-of-care intervention to improve neuropsychiatric behaviors in people with dementia.

The PI and faculty advisor will assess the severity (intensity) of reported AEs according to the NCI CTC. If a participant experiences an event not detailed by the NCI CTC, the following guidelines will be used to analyze severity:

- Mild: symptoms or signs exist and may require treatment, but are transient and easily tolerated.
- Moderate: treatment is required and continued monitoring of event is prescribed to avert participant discomfort.
- Severe: event requires treatment and continued monitoring is prescribed to prevent incapacitating or life threatening effects to the participant's health.
- Life threatening: when the participant is, in the opinion of the Investigator, at immediate risk of death from the event as it occurs, or if the event requires immediate medical treatment and continued monitoring. Note that this definition does not include an event that, had it occurred in a more serious form, might have caused death.
- Fatal: Death resulted from AE.

All adverse events occurring during the study observed by study personnel or reported by the participant (whether or not attributed to study procedures or interventions), will be recorded in the subject electronic record. Medically significant adverse events considered related to the study procedures or interventions by the faculty advisor will be followed until resolved or considered stable. It will be left to the faculty advisor's clinical judgment whether or not an adverse event is of sufficient severity to require the participant's removal from treatment. A participant may also voluntarily withdraw from treatment due to what he or she perceives as an intolerable adverse event. If either of these occur, the participant must undergo a Termination (early discontinuation) visit, and be given appropriate care

under medical supervision until symptoms cease or the condition becomes stable.

In order to adhere to all applicable laws and regulations for reporting an SAE, the PI will formally notify the UK IRB within 24 hours or the study site staff becoming aware of the SAE. Adverse events will be coded according to body system using MedDRA. A final medical review and sign off on all codes by a designated reviewer within the ADCS will ensure accuracy and consistency.

In this study, we do not anticipate moderate, severe, life-threatening or fatal AEs.

c. Plans for Safety Review: A methodical review of all procedures will be an integral part of each research team meeting. This review will include discussion of the protocol to ensure adherence, discussion of procedures to insure confidentiality is maintained and that data are collected with minimal risk for violations of confidentiality. A meeting involving the PI, faculty advisor, co-investigators, and lay coworkers will be called if an unexpected adverse event occurs.

d. Plans for Data Quality: The research design, methods and procedures have been reviewed by all members of the research team, all of whom have indicated their approval of the processes as delineated and believe that this research project will yield quality data that will generate new knowledge. Detailed operationalization of this plan will be done as a team to assure data quality.

e. Reporting Mechanisms: Reporting for this study will include an annual report to the University of Kentucky IRB, with appropriate updates and reports in the event of an adverse event(s). SAEs will be reported to the UK IRB within 24 hours of notification as mandated by this regulatory body.

f. Plans for Modification or Termination of Study: If SAE or frequent AE's beyond mild severity occur in more than 30% of participants, we will review research intervention causes and modify intervention to minimize risk. We will withdrawal patients with AE's above moderate severity if AE is associated with study intervention, as this will indicate risks may exceed potential benefits of this study.

[Back to Top](#)

**Subject Complaints:** Describe procedures (other than information provided in consent document) for handling subject complaints or requests for information about the research. The procedures should offer a safe, confidential, and reliable channel for current, prospective, or past research subjects (or their designated representative) permitting them to discuss problems, concerns and questions, or obtain information.

Subjects will be provided with the PI's email and phone numbers for contact if concerns or complaints arise. A confidential meeting between the PI and participants will be arranged using Zoom, video call, or telephone call with the subject to address concerns and complaints. Subjects may also speak with SBCoA social workers or Clinic director with concerns. If subjects have any questions or complaints about the research study they may contact staff in the Office of Research Integrity at the University of Kentucky at [contact].

Are you recruiting or expect to enroll **Non-English Speaking Subjects or Subjects from a Foreign Culture?** (does not include short form use for incidentally encountered non-English subjects)

Yes  No

Non-English Speaking Subjects or Subjects from a Foreign Culture

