There is minimal risk involved in participation of this study. Potential for minimal risk is associated with possibly sensory system overload associated with interventions. Signs of sensory overload include neurophysiological changes (sweating, dizziness, changes in balance, pallor, pupil dilation, yawning), emotional and behavioral changes (fearful responses, avoidance, irritability, anxiety, angry outbursts, aggression, agitation), and cognitive changes (increased confusion, decreased orientation to time, place, self, etc.), and decreased attention span (more than typical). Monitoring of sensory overload will be monitored by caregivers following training of

intervention techniques, psychosocial stress and burden to the individual with dementia and their caregiver during and the presence of the researcher during observation. Interventions may include topical lotions which may cause skin irritation, rash, or dermatitis. Caregivers will be trained to observe patient for any signs of discomfort, sensory overload, or skin irritation, distress or anxiety. If a participant/caregiver shows signs of distress or anxiety, the researcher will provide the participant/caregiver with a break. If the participant wishes to proceed then another topic may be discussed, if not the interview or observation will be rescheduled for a different date.

[Back to Top](#)

**Safety Precautions:** Describe the procedures for protecting against or minimizing any potential risks, *including risks of breach of confidentiality or invasion of privacy*. Where appropriate, discuss provisions for ensuring necessary medical or professional intervention in the event of adverse events, or unanticipated problems involving subjects. Also, where appropriate, describe the provisions for monitoring the data collected to ensure the safety of subjects. If vulnerable populations other than adults with impaired consent capacity are to be recruited, describe additional safeguards for protecting the subjects' rights and welfare.

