The procedures for protecting against and minimizing any potential risks of breach of confidentiality or invasion of privacy during the research will require each individual with dementia, their LAR, and the caregiver to review and sign the consent and confidentiality agreements. All study conduct will occur using procedures outlined and validated by the University of Kentucky Telemedicine office. Contact information for [name] (SBCOA Clinical director) and SBCOA social workers will be kept on file and accessible during data collection in the field in case issues or concerns arise during intervention visits. Collected data will be de-identified and all data will be kept in a password-protected computer for a period of six years, then destroyed via deletion of files.

**Benefit vs. Risk:** Describe potential benefits to the subject(s); include potential benefits to society and/or general knowledge to be gained. Describe why the risks to subjects are reasonable in relation to the anticipated benefit(s) to subjects and in relation to the importance of the knowledge that may reasonably be expected to result. If you are using vulnerable subjects (e.g., impaired consent capacity, pregnant women, etc...), justify their inclusion by describing the potential benefits of the research in comparison to the subjects' vulnerability and the risks to them. For information about inclusion of certain vulnerable populations, see the IRB/ORI Standard Operating Procedure for Protection of Vulnerable Subjects [C3.0100] [\[PDF\]](#).

There are no direct benefits to subjects. Risks to participants, both caregivers and those with dementia, are minimal, including possible discomfort with sensory-based intervention implementation.

**Available Alternative Treatment(s):** Describe alternative treatments and procedures that might be advantageous to the subjects, should they choose not to participate in the study. This should include a discussion of the current standard of care treatment(s).

Not applicable.

[Back to Top](#)

**Research Materials, Records and Privacy:** Identify the sources of research material obtained from living human subjects. Indicate what information (specimens, records, data, genetic information, etc.) will be recorded and whether use will be made of existing specimens, records or data. Explain why this information is needed to conduct the study.

*Return of Research Results or Incidental Findings (if applicable):*

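### Choking on snacks and falls during exercise are anticipated, but the risk text and caregiver watch list omit both, and no shown text links the chart review to withholding kit food

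*Combined protocol and SAP*

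**What the plan says.** Item 2 of the periodic review in the Data and Safety Monitoring Plan lists the kit-related problems that the team expects. Two are mechanical hazards: "Snacks-possible choking hazard" and "Exercise cards-muscle soreness, fall during exercise".

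Potential Risks describes sensory overload, psychosocial stress and skin reactions to lotion. On training it says: "Caregivers will be trained to observe patient for any signs of discomfort, sensory overload, or skin irritation, distress or anxiety". Its only described response to distress is a pause given by the researcher, or a rescheduled interview or observation.

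Safety Precautions deals with confidentiality, telemedicine procedures and clinic contacts, whose details "will be kept on file and accessible during data collection in the field in case issues or concerns arise during intervention visits".

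The screening visit (Research Procedures) reviews charts for known allergens, chronic conditions and medications. It also examines the mouth and teeth, cranial nerves and gait. The exclusion criteria cover lotion or fragrance allergy and people who are wheelchair- or bed-bound. They do not mention food allergy or swallowing.

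Events are picked up at weekly video checks. At team meetings, "Adverse events will be reviewed to determine if changes in the protocol are indicated".

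**The concern.** Kits are used at home with the caregiver giving or supervising the session, and participants have moderate to severe dementia. The informed consent section says they may also have communication deficits. Between weekly contacts, safety rests on the caregiver. The plan names two hazards that could seriously harm a frail person, yet the training text shown leaves both out and gives no instruction to stop and report. A caregiver would probably notice a fall or a choking episode. What is missing is a stated expectation of what to do next. For food, the facts that would identify someone at risk are partly collected at screening, but no shown step acts on them when the kit is assembled.

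**Working it through.** The plan gives no figure to reproduce. The check follows each hazard through the text and then works out exposure and time to detection.

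**1. From named hazard to stated control**

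| Hazard in the monitoring plan | In Potential Risks? | On the caregiver watch list? | Stated selection or kit control |
|---|---|---|---|
| Skin reaction to lotion | Yes | Yes | Lotion or fragrance allergy excluded |
| Fall during exercise | No; dizziness and altered balance appear only as overload signs | No | Wheelchair- or bed-bound people excluded; gait examined; arm movements used in the standard kit if walking needs assistance |
| Choking on snacks | No | No | None specific to food; mouth and teeth examined and allergens recorded, with no linked action |

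The lotion row shows that the team carried one kit hazard all the way to training and eligibility. Falls are partly controlled through selection. Choking has no stated control of its own.

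**2. Choice of kit items**

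The Individualized Environmental Design Protocol bases items on sensory preference and behavioral concerns, using an attached decision tree and sensory mode plans. No medical filter on food appears in the shown text. The standard kit lists no food; snacks appear only in the monitoring plan.

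**3. Exposure**

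Inputs: 4 weeks = 28 days; 10 participants per arm; three sessions a day in the standard arm; two scheduled sessions plus one as needed in the individualized arm.

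- Individualized arm: 2 × 28 = 56 to 3 × 28 = 84 sessions per participant, or 560 to 840 for ten, if every kit holds food and it is used each time. The figure is 0 if no kit holds food.
- Standard arm, movement: 3 × 28 = 84 per participant, or 840 for ten, if every session includes movement. Food: none stated.

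These are counts of opportunities at full adherence, not event rates.

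**4. When responsible staff would know**

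Visits 4–8 fall at the end of each intervention week and record adverse events, so an event should reach staff within about 7 days. Subject Complaints also gives participants the PI's phone and email.

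**5. What a mild event triggers**

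Unexpected events "are those not specified in the IRB-approved research protocol or informed consent document". Choking and falls are listed, so on that wording a mild one does not call the ad hoc team meeting. The 24-hour report covers serious events only. The modification rule counts serious events or frequent events beyond mild in more than 30% of participants: 0.30 × 30 = 9, so at least 10. A mild event is still recorded, graded by the PI and faculty advisor, and reviewed at the next scheduled meeting.

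**The case against.** The strongest reply is that the missing rules may sit in files not shown. The kit list, decision tree, sensory mode plans, detailed protocol and consent forms are where a food or swallowing rule would naturally be. This stands, and it means that nobody can say from this text that no rule exists. It does not explain why the risk section and watch list differ from the plan's own hazard list.

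Second, signs of discomfort or distress plausibly include choking, and the eligibility criteria let a clinician reject anyone physically unsuitable. Both are fair. Neither tells a caregiver to stop and report, and neither is a rule about food.

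Third, a reader might infer that the plan already gives behavior change a prompt escalation that choking and falls lack, since item 1 says "If substantial behavioral change is noted by caregiver or patient report, this behavior change will be reviewed with faculty advisor". The text does not support that. Item 1 sets no time limit, and both items belong to review carried out at meetings.

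Fourth, a reader might take the meeting calendar ("bi-weekly meetings for the first two months of enrollment, then monthly for four more months, and quarterly thereafter") as the delay before anyone responds. Reading bi-weekly as every two weeks, the gaps are 14, 365.25/12 = 30.4 and 365.25/4 = 91.3 days. But these are intervals between meetings. The PI shares responsibility for safety, weekly contact considers whether to modify or stop the intervention, and nothing prevents the PI from changing other kits at once. The number of dyads starting in the quarterly phase is also unknown.

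Finally, the value of one event as a warning for others is limited. If the ten individualized dyads were spread over 6 to 12 months (an assumption), only 10 × 28/365 = 0.8 to 10 × 28/183 = 1.5 would be in intervention at once, and their kits need not share the item.

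**Conclusion.** The point holds as a mismatch within the shown text. Two hazards that the team anticipates are absent from the stated risks and the caregiver watch list, no precaution is given for either under Safety Precautions, and the screening data are not tied to any decision on kit food. It should be treated as a cheap improvement to participant safety. It changes no endpoint, estimate or analysis.

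Its size cannot be put as a rate. Snack exposure could be nil, because the only kit itemized in the text lists no food. The fall part does not depend on food, since movement is in the standard kit. The conclusion assumes that the unseen attachments do not already contain the instructions; if they do, only the mismatch between sections remains. The documents do not support a claim that events go unknown to responsible staff for weeks or months: weekly contact limits that to about 7 days.

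**What to change.** 1. Add choking and falls to Potential Risks and to the caregiver observation list. At the Visit 3 training, tell caregivers to stop the session and report either event to the PI, using the contact details already provided under Subject Complaints.
2. If kits contain food, withhold it from participants with known dysphagia or a relevant food allergy, using the chart review already planned at screening. If kits contain no food, delete snacks from the monitoring plan.
3. Optionally, add a new step: when a choking episode or fall during kit use comes to light at a weekly check, the PI tells the faculty advisor, and the two consider whether other kits need changing. No full-team meeting is needed.

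The cost is a few sentences of text, a few minutes of training, an occasional review by two people, and some kits without a food item. Nobody is excluded.

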Participants will be selected with assistance from Sanders Brown Center on Aging (SBCoA) staff using the University of Kentucky Alzheimer's Center Longitudinal participant database (IRB# 88-0102-F2L [[name], PI]). University of Kentucky Alzheimer's Disease Center Clinical Core Leader, [name], has approved access to and use of the University of Kentucky Alzheimer's Disease Center Community Registry database, which is located at the SBCoA Clinic, [name]. The database follows 200-300 volunteers who live in the local community around SBCoA Clinic for longitudinal data collection purposes. Participants with cognitive impairment are primary targets for data tracking for the database. Each participant in the database has corresponding information for primary caregivers, which is also maintained in the database. All cognitively impaired database enrollees and their caregivers have agreed to be contacted by SBCoA associates for invitation to participate in additional research projects. Annual confirmation is obtained by the center to ensure participants continue to permit contact via phone calls or other methods from researchers and staff at SBCoA for notification, explanation, and invitation to additional research opportunities offered by the University of Kentucky.

Patients of the Kentucky Neuroscience Institute with memory impairment may also be contacted for participation of this study. Upon identification of eligible participants, the KNI medical team will determine patient interest to be contacted by study personnel and notify [name] (PI) to follow up with contact to potential participants and/or the study flyer will be mailed or emailed to eligible patients with request to contact study personnel if interested in study participation.

Primary measures:

Feasibility will be assessed by monitoring of protocol adherence and behavior change.

- Caregivers will be responsible for providing treatment protocols throughout duration of treatment window. Adherence to the protocol will be kept and measured using the behavioral journal and intervention adherence log
- Weekly check-ins with the caregivers will provide opportunity to review adherence and reactions to the protocol, as well as assess for adverse reactions, need for modification, or discontinuation. If the investigator finds that the participant is noncompliant, the PI

may remove the participant from further participation in the study.

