Informed consent will be collected via several ways. The electronic or hard copy IRB-Stamped informed consents will be emailed/mailed to the person with dementia's legally authorized representative (LAR) or the patient with dementia and their care advocate if LAR is not established (patient consent form), and their identified caregiver (caregiver consent form). An electronic form e-Consent will be emailed to both individuals (LAR and Caregiver) and required for signature using REDCap technology. This form will be signed prior to the screening visit, or after thorough review during the screening visit, along with assent obtained from the person with dementia. The assent form will be discussed and used with the patient via Zoom video conferencing during screening visit. Verbal confirmation of understanding and willingness to participant will be sought. If they are unable to provide verbal communication, non-verbal cues such as head nodding (described in Form T) will be collected. If non-verbal cues are unable to be collected, consent will be deferred entirely to the LAR.

A copy of the consent form will be emailed or mailed to the participants prior to Visit 1. LAR's, participants with dementia, and caregivers will be advised that participation is strictly voluntary, and they can withdraw from the study at any time. Participants will be assured that participation or nonparticipation of this study will have no direct effect on enrollment or participation of SBCoA program and healthcare services.

A waiver of documentation of informed consent will be used for administration of the Situational Assessment of Activity and Function (SAAF) survey. A link will be emailed to caregiver participants with a cover letter explaining the assessment. Participants are not required or obligated to respond to the email or survey and all responses will be deidentified. Completion of the assessment and feedback via email to the study PI regarding participants' experience with the assessment will indicate implied consent.

**Research Procedures:** Describe the research procedures that will be followed. Identify all procedures that will be carried out with each group of subjects. Differentiate between procedures that involve standard/routine clinical care and those that will be performed specifically for this research project.

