Once eligibility is confirmed, the research assistant will email a REDCap link to the caregiver for the Zarit Caregiver Burden and the Adult Sensory Profile, Actigraph and charger, and a copy of consent forms to the participant's caregiver. The PI will complete the COPM on visit 1, and provide caregiver and participant with Actigraph wear and care instructions. The VABS will be emailed to the caregiver via a confidential link through Pearson Publishing.

Subjects will be randomized to treatment arms by the statistical team. Participants will be randomized into one of the three groups: control, standard environmental design protocol, individualized environmental design protocol. Recruitment will be ongoing until all groups have 10 participants. In the event of drop out or early termination (causes will be recorded), researchers will recruit for replacement participants so that the study is completed with 30 entire study duration cases.

Visit 2 will consist of baseline assessment. A research assistant or the PI will complete the MOCA, with the participant with dementia. The caregiver will complete the NPI. Following Visit 2, an occupational therapist will be provided results of the COPM and ASP for participants of the individualized treatment arm. A sensory protocol will be developed based on assessment results following predetermined guidelines. All intervention materials for all study participants will be mailed to caregivers within 4 days of Visit 2. Upon receipt of intervention supplies, caregivers will contact the PI or occupational therapist for study initiation. Visit 3 will provide caregiver training for intervention use and initiation of Actigraph use. Adverse events since Visit 2 will be recorded. Visit 3 marks day 1 of intervention implementation. Participants will mail Actigraph back to UKADC in provided pre-paid envelop following week one of intervention.

Visits 4-8 will be scheduled at the end of each week following Visit 3. The PI, occupational therapist, or research assistant will record concurrent medication, and adverse events. With the caregiver, the interviewer will review behaviors observed by the caregiver, the behavior journal, compliance and acceptance of the intervention by the caregiver and the person with dementia. Actigraphs will be mailed from UKADC to participants, and patient will be asked to wear actigraph for last week of intervention window.

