## Statistical Analysis

Participants' characteristics were compared among the three arms using analysis of variance (ANOVA) for continuous measures and chi-square tests or Fisher's exact for categorical measures. The analysis of the primary endpoint used a chi-square test to compare the proportion of participants completing at least 75% of the video sessions among the study arms. The analysis of all secondary and exploratory endpoints relied on a modified intention-to-treat (mITT) strategy in which participants were included in the analysis only if the dyad completed at least one video session. For those endpoints, the main analysis tool was ANCOVA in which the mean value of an endpoint at the end of the intervention period was adjusted for baseline and then compared among the study arms. Sensitivity analyses were conducted in which multiple imputation was used for missing responses at the end of the intervention period (regressed on baseline) and in which the list of covariates included age of the person with AD at baseline and gender of the caregiver when appropriate. These sensitivity analyses did not change any of the conclusions drawn from the reported ANCOVA in Table 3 and are not reported here. A further sensitivity analysis included the measurements made at the four-week follow-up and relied on ANCOVA to compare the profile of responses at the end of the intervention and at the four-week follow-up each adjusted for baseline. This analysis did not change the conclusions drawn from Table 3 and is not reported here. All analyses were done using PC-SAS, Version 9.4.

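### The plan does not keep dyads in outcome follow-up once the intervention stops, so the behaviour comparison leans towards those who stayed

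*Combined protocol and SAP*

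**What the plan says.** Rules on stopping:

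- **Data and Safety Monitoring Plan, b. Adverse Events.** The rule covers removal on clinical judgment and one kind of voluntary stop: "A participant may also voluntarily withdraw from treatment due to what he or she perceives as an intolerable adverse event". In both cases: "If either of these occur, the participant must undergo a Termination (early discontinuation) visit". The assessments at that visit are not listed.
- **Data and Safety Monitoring Plan, f. Plans for Modification or Termination.** "We will withdrawal patients with AE's above moderate severity if AE is associated with study intervention". Whether this means withdrawal from treatment or from the study is not said.
- **Research Description, Study Design, primary measures.** If a participant is found noncompliant, the PI "may remove the participant from further participation in the study".
- **Informed Consent Process.** Participants are told that "participation is strictly voluntary, and they can withdraw from the study at any time". Nothing is said about outcome data after that.
- **Research Procedures.** After drop-out or early termination, "researchers will recruit for replacement participants so that the study is completed with 30 entire study duration cases". Visit 9 (week 4) and Visit 10 (week 8) carry the NPI, COPM, VABS and Zarit. The schedule of events is referred to a separate detailed protocol, which is not among these documents.

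Rules on analysis:

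- **Data Analysis (protocol).** A per-protocol analysis at 75% adherence or more, in a study described as not fully powered, with exploratory and descriptive behaviour results.
- **Statistical Analysis (SAP).** The primary endpoint is the proportion completing at least 75% of video sessions. For all other endpoints the set is modified intention-to-treat: "participants were included in the analysis only if the dyad completed at least one video session". The main model is ANCOVA of the end-of-intervention value adjusted for baseline. Multiple imputation of missing end-of-intervention values, with baseline as predictor, is a sensitivity analysis. A further ANCOVA adds the four-week follow-up, with no imputation described.

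**The concern.** Stopping an intervention and leaving a study are different events. If a plan merges them, outcomes go missing for the dyads whose experience of the intervention was probably least typical, and a randomised comparison drifts towards a comparison of those who tolerated their assignment.

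Here the two could plausibly be linked. Potential Risks lists irritability, anxiety, aggression and agitation among the signs of sensory overload. The NPI-Q domains include irritability, anxiety and agitation. One foreseen harm therefore overlaps with what the outcome scale measures, and control dyads are not offered a sensory kit until after the follow-up visit. If some dyads stop because behaviour worsened after baseline, adjusting for baseline cannot recover what was not measured.

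**Working it through.** **1. The plan's own figure.** 3 arms x 10 = 30, as stated. The documents give no SD, effect size, stopping rate or dropout allowance, so there is no power or bias figure to reproduce.

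**2. A stopping dyad followed through the text.**

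- Stop for an adverse event: a Termination visit of unlisted content. Visits 9 and 10 are neither promised nor ruled out.
- Noncompliance: possible removal from the study itself, so poor uptake of the intervention can end follow-up.
- Either route, if counted as early termination: a replacement is recruited, and the dyad does not count towards the 30.
- No visible passage asks a stopped dyad for the week-4 or week-8 assessments.

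**3. The same dyad in the SAP.** With one video session it is in the modified intention-to-treat set. Without an end-of-intervention value it contributes nothing to the main ANCOVA. Imputation from baseline gives it the value expected for its baseline, so the reason for stopping and the course after baseline play no part. For week 8, no imputation is described.

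**4. Illustrative size.** Let f be the share of an arm that stops and d the amount by which stoppers are worse than stayers with the same baseline, in SD. If stayers average S, the full arm averages (1 - f) x S + f x (S + d) = S + f x d, where larger is worse. The stayers' mean is too favourable by f x d. Imputing from baseline amounts to setting d = 0. The ranges f = 10-30% and d = 0.5-1 SD are assumptions.

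| f | f x d, d = 0.5 | f x d, d = 1.0 | Outcomes from 30 randomised, completers only: 30 x (1 - f) | Randomised to reach 30 completers: 30 / (1 - f), rounded up |
|---|---|---|---|---|
| 10% | 0.05 | 0.10 | 27 | 34 |
| 20% | 0.10 | 0.20 | 24 | 38 |
| 30% | 0.15 | 0.30 | 21 | 43 |

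Replacement restores the count of 30. It leaves f and d, and so the bias, unchanged.

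**5. Direction.** The bias in an arm difference is (f x d in the active arm) minus (f x d in control). With 30% and 1 SD in the active arm against 10% and 0.5 SD in control, it is 0.30 - 0.05 = 0.25 SD in favour of the active arm. With the two arms exchanged, it is 0.25 SD against it. With equal values it cancels.

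**The case against.** A reader might infer more than the documents say, and the case against that stronger reading is good.

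- **That outcome collection ends by rule.** The adverse-event section speaks of stopping treatment and requires a visit. That visit could include the outcome scales, and the detailed schedule, which was not supplied, may say so. This objection stands: the gap is in the visible text, and no prohibition is stated.
- **That the Termination rule covers every stop by choice.** It covers adverse-event stops only. General withdrawal is described as leaving the study, and some of those dyads may also decline further data collection. This stands.
- **That the analysis is confined to stayers.** The SAP's set admits early stoppers, and its imputation analysis is reported as not changing the conclusions. This stands in part. The main model still needs an observed value, and imputation from baseline cannot test stopping that depends on what happened after baseline.
- **That sensory overload is the expected reason to stop, so the bias favours the active arms.** The monitoring plan's anticipated concerns are skin reaction, muscle soreness, falls, choking, headache and strain, and it anticipates no events of moderate severity or worse. Stopping for a rash need not mean a worse NPI. Control dyads might also leave as behaviour worsens. This stands: the direction is unknown.
- **That the bias is large.** Assuming a baseline-outcome correlation of 0.6, the standard error of a pairwise ANCOVA difference at 10 per arm is sqrt(1 - 0.6^2) x sqrt(2/10) = 0.8 x 0.447 = 0.36 SD. The whole illustrative range lies below one standard error. This stands and limits the severity, although a systematic shift does not average out as random error does.

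**Conclusion.** The concern holds in a limited form. The visible plan does not provide for outcome follow-up after the intervention stops, and its rules on removal and replacement treat stopping as leaving. The SAP's modified intention-to-treat set and baseline-only imputation soften the consequence for week 4 but do not remove it. For week 8 no imputation is described. The protocol's per-protocol set leans the same way and differs from the SAP's set, so the two need reconciling.

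The figure of 0.05-0.30 SD in one arm's mean rests wholly on assumed stopping rates and an assumed stopper-stayer gap. The net effect on an arm difference could go either way.

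The point should be fixed, but it is not critical: the SAP's primary endpoint is session completion, and the endpoints affected are those it treats as secondary or exploratory. Study Design does list behaviour change and the Zarit under primary measures, which is a further reason to collect them from every randomised dyad. The documents do not support saying that stoppers have no week-4 or week-8 data.

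**What to change.** - In Study Design (removal for noncompliance), Research Procedures (replacement) and items b and f of the monitoring plan, state that stopping the intervention does not end outcome collection. In item f, say whether withdrawal is from treatment or from the study.
- Ask the caregiver for the Visit 9 and Visit 10 assessments after any stop, unless consent for data collection is withdrawn.
- List the Termination visit's assessments and include the Visit 9 caregiver outcomes, recorded at their actual date.
- In the SAP, analyse all randomised dyads with outcome data in the arm to which they were randomised.
- If collection is finished, as the SAP's past tense suggests, report stoppers and missing outcomes by arm and reason. Add a sensitivity analysis that lets stoppers differ from stayers with the same baseline, for example over d = 0.5-1 SD and separately by arm, at week 4 and week 8.

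The cost is small. If 10-30% stop, that is 1-3 dyads of 10 in each arm, or 3-9 across three arms. Two visits each makes 6-18 remote assessments with existing staff and instruments. When treatment is stopped remains a clinical decision and is not addressed here.
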